4.0 Study Intervention(s)/Investigational Agent(s)

1. Description: A multigene panel comprised of genes with known functionality in the heart, vasculature, and kidney, that are known to influence BP. This study will be performed as a retrospective study on patients within the Fairview Health System. Patients will be those who have been previously diagnosed with hypertension and have a history of blood pressure control (<140/<90 for two consecutive office measures. The study will involve collection of a buccal swab (can be done at the patient’s home, by the patient) and a clinical chart review of the patient’s hypertension and medication history. From the buccal swab we will assess 18 SNPs in 11 genes (2) SNPs in ADRB1, (2)

PROTOCOL TITLE:

VERSION DATE:

SNPs in ADRB2, (1) in SCNN1A, (1) in ADD1, (2) in SLC12A3, (3) in WNK1, (1) in ACE, (3) in AGT, and (1) each in AGTR1, CYP2D6*4 and REN) with known functionality in the liver, heart, vasculature, and kidney.

2. Drug/Device Handling: The device used for sample collection is a buccal swab kit that gently removes cells from the inside of the cheek. The Geneticure kit contains two buccal brushes and two tubes of lysis buffer. The patient swabs their left cheek and deposits the end of the swab in the lysis buffer, then does the same for the right cheek. This swab is placed (by the patient) in lysis buffer (a small tube) and shipped to the study site, if collected off site. The swab is then shipped to the University of Arizona Genomics core facility for DNA extraction, quantification, and assessment of the genes listed above. The study is retrospective in nature and the DNA assessment will not influence prescribing, i.e. no drugs will be changed based on this analysis for the patients. No identifying information will EVER accompany the kit to the genetic testing facility.
3. IND/IDE: In-vitro diagnostic device and exempt from IDE.
4. Biosafety: N/A

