Secondary Objective(s)	
1. Number of medications needed to obtain control2. Time to control3. Number of office visits to control4. Side effects from hypertension therapy5. Hypertension associated adverse events during the course of treatment
Research Intervention(s)/Investigational Agents	Association between blood pressure control and genetic variants important in blood pressure regulation.
IND/IDE # (if applicable)	
Investigational Drug Services # (if applicable)	
Study Population	Hypertensive patients who have achieved BP control
Sample Size (number of participants)	Up to 2000
Study Duration for Individual Participants	Less than one day

PROTOCOL TITLE:

VERSION DATE:

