1.0 Objectives

Purpose: To assess the effectiveness of the use of a patient's genes to predict which hypertension therapy is successful, as measured by:

- 1. Level of blood pressure control (<140/<90)**
- 2. Change in blood pressure from baseline to control**
- 3. Number of medications needed to obtain control**
- 4. Time to control**
- 5. Number of office visits to control**
- 6. Side effects from hypertension therapy**
- 7. Hypertension associated adverse events during the course of treatment**

2.0

Background

1. Significance of Research Question/Purpose:

Hypertension is known to have a strong heritable component. Previous work has demonstrated that sons of hypertensive patients are more likely to be hypertensive when compared to sons of normotensive individuals. Additionally, monozygotic twins are more likely to share hypertension than dizygotic twins who are more likely than non-twin siblings to share hypertension. Each of these previous studies demonstrate that genetics plays a role in the development of hypertension. For each major class of drugs (diuretic, vasodilator, and β -blocker) the effectiveness rate ranges from 40-60%. Contrary to common belief, even a small ~10-20% of patients have an increase in blood pressure with a given anti-hypertensive medication. These effectiveness rates go far beyond adherence in that these previous trials have controlled for medication adherence. In addition to this controlled studies, epidemiologic data has demonstrated that 40% of patients who take their medication, as prescribed by their clinician, do not have their blood pressure under control.

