3.0 Study Endpoints/Events/Outcomes

1. Primary Endpoint/Event/Outcome:

To assess the effectiveness of the use of a patient’s genes to predict which hypertension therapy is successful, as measured by:

1. Level of blood pressure control (<140/<90)
2. Change in blood pressure from baseline to control

2. Secondary Endpoint(s)/Event(s)/Outcome(s):

Blood Pressure control with respect to:

1. Number of medications needed to obtain control
2. Time to control
3. Number of office visits to control
4. Side effects from hypertension therapy
5. Hypertension associated adverse events during the course of treatment

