- Review Inclusion/Exclusion Criteria. The investigator and/or designee will review all criteria to determine if the subject is eligible for enrolment. Eligibility of all subjects must personally be confirmed by the Investigator and will be documented on the CRF.

Enrollment

- Assign Identification Number to Eligible Subjects.

Chart Review

- Record demographics, antihypertensive medical history and most recent blood Pressure. Data will be documented in the source document and recorded on the patient demographic form, including but not limited to the following:
 - Age
 - Sex

PROTOCOL TITLE:

VERSION DATE:

- Height
- Weight
- Race
- Ethnicity

(additional data for collection is included in the attachment entitled "metrics")

Specimen Collection

- Collect Buccal Specimen.

Subject Numbering

Subjects meeting the criteria for enrollment (and their specimens) will be identified by unique numbers that will be assigned sequentially by order of enrollment. The pre-assigned investigational site number will be prefixed with GCE and the identification number and separated by a hyphen (e.g., GCE-001etc.). Throughout the descriptions within the protocol the A swab will be referring to the swab that has originated from the right cheek, while the B swab will be that that has originated from the left cheek. To further clarify. Subject GCE-001 will be given two barcoded tubes. These barcode numbers should be recorded for each patient. These will also be recorded as originating from the right cheek (A) or left cheek (B).

At no time should any study paperwork or specimens be marked with the subject's name or any other traceable identifier except for the informed consent form, which is signed by the subject and kept at the site. At no time should the original (signed) or a copy of this form be collected by the Sponsor or its representative.

2. Follow-Up: Data will be collected for up to one year.

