16.0 Data Management

1. Data Analysis Plan:

The Investigator is responsible to ensure the accuracy, completeness, and timeliness of reported data.

PROTOCOL TITLE:

VERSION DATE:

All data will be compiled within the Fairview system on secure servers. De-identified final data may be sent to Geneticure using a secure, password-protected Excel spreadsheet on a server that is only accessible to IRB-approved personnel and is fully auditable. The database will be validated prior to use in the study. All required data will be recorded on CRFs or paper facsimiles. Data collected within the CRFs will be supported by source documents as appropriate and may be updated to reflect the latest observations on the subjects participating in the study. Corrections to the source documentation will be made in a manner that does not obscure the original entry and will be dated and initialed by the Investigator or assigned designee. It is important for data entry to occur in a timely manner, therefore, data collected on source documents should be transferred into CRFs as soon as possible following study visits.

All data will be coded for statistical analysis (i.e. drug classes will be coded numerically and genotypes will be coded numerically). Subject's raw genetic data will be entered into the Geneticure for Hypertension algorithm. All data will be analyzed with SPSS v.20. Normality of the data will be assessed using Levene's test prior to statistical analysis and any correction for non-normal data distribution will be used. Descriptive statistics will be computed (average time for blood pressure control, average number of visits to the clinician for blood pressure control, age, height, weight, BMI, etc.).

Data will be initially analysed following the collection of samples/data from up to 600 subjects. Statistical tests will be corrected for the number of tests run (preservation of alpha). Ordinary least squares regression via univariate modelling will be used to estimate the magnitude of linearity between drug class that yielded the best blood pressure control and genetic profile of the subject. Multiple regression analysis will be performed to determine the impact of confounding variables (height, weight, age, race) on blood pressure control. For all statistical analyses an alpha level of 0.05 will be used to determine statistical significance.

Missing Data

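### If entry is limited to patients already below 140/90, primary endpoint 1, which uses the same threshold, is constant or weakened; the eligibility list has no such limit, and the two must be reconciled

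*Combined protocol and SAP*

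**What the plan says.** Two places define the sample by control already reached. The Study Summary gives the population as "Hypertensive patients who have achieved BP control". Section 4.0, item 1, says: "Patients will be those who have been previously diagnosed with hypertension and have a history of blood pressure control". It specifies that they "have a history of blood pressure control (<140/<90 for two consecutive office measures", and sets no time window for those two measures.

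Section 9.0 differs. Its criteria cover age, body mass index, at least one year since diagnosis, at least six months on the same drug class or classes, and the permitted classes. The only pressure limit is an exclusion for systolic above 190 or diastolic above 120 in the previous six months. Nothing requires control. Section 5.0, under Screening, refers the reader to this list as the full set of eligibility rules.

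Section 3.0 makes "Level of blood pressure control (<140/<90" the first primary endpoint, with no reading or time point named. The second is "Change in blood pressure from baseline to control". Secondary endpoints 1 to 3 (medications, time and office visits) are also counted up to control. Under Chart Review, Section 5.0 asks staff to "Record demographics, antihypertensive medical history and most recent blood Pressure".

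For analysis, Section 16.0 relates genetic profile to the drug class that gave the best control, and adds: "Multiple regression analysis will be performed to determine the impact of confounding variables (height, weight, age, race) on blood pressure control". Its sample size rests on mean arterial pressure (MAP) under diuretic treatment in two WNK-1 genotype groups.

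**The concern.** The stated aim is to find out whether genes predict which treatment succeeds. Section 2.0 itself reports that "40% of patients who take their medication, as prescribed by their clinician, do not have their blood pressure under control". A sample restricted to patients with documented control leaves out those who never reached it, and they carry part of any genotype signal. When the entry rule and a primary endpoint share one threshold, selection acts directly on the outcome. At best the contrast is diluted, and at worst the endpoint has no variation to analyse. The power statement would then also describe a different population from the one enrolled. Analysis cannot repair this once only controlled patients have been recruited.

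**Working it through.** **Inputs from Section 16.0.** MAP 97.6 mmHg (functional WNK-1) and 100.8 mmHg (non-functional), pooled SD 12, alpha 0.05 (taken as two-sided), power 0.80, 300 per group.

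**1. The plan's own figure.** n per group = 2 × (1.96 + 0.84)² × 12² / 3.2² = 221. The stated 300 does not follow from its inputs. At 300 per group, power = Φ(3.2 / (12 × √(2/300)) − 1.96) = Φ(1.31) = 90%. I keep 300 as the planned size.

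**2. The control threshold on the MAP scale.** At 140/90, MAP = (140 + 2 × 90)/3 = 106.7 mmHg. Any controlled reading lies below this, so the cut is necessary for control but not equivalent to it, and what follows is approximate.

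**3. No selection.** The share below 106.7 is Φ(9.07/12) = 77.5% against Φ(5.87/12) = 68.8%, a difference of 8.8 points. Power at 300 per group = Φ(0.0875 / √[(0.775 × 0.225 + 0.688 × 0.312)/300] − 1.96) = 68%.

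**4. Section 4.0 governs, endpoint read as control ever achieved.** Every patient qualifies by being controlled, so the result is 100% v 100%. A regression on that outcome cannot be fitted.

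**5. Section 4.0 governs, MAP taken at a reading that had to be controlled.** Truncating each normal distribution at 106.7, with a = (106.7 − μ)/12 and λ = φ(a)/Φ(a), the mean is μ − 12λ and the SD is 12√(1 − aλ − λ²). The means are 92.96 and 94.62 (difference 1.66) and the SDs 8.96 and 8.34 (pooled 8.66). The standardized effect falls from 0.267 to 0.192, about 425 per group are needed for 80% power, and power at 300 is 65%.

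**6. Section 4.0 governs, endpoint read from a later, most recent reading.** The documents give no within-person variability and no number of earlier readings, so both are assumptions. Let w be the within-person SD and √(144 − w²) the between-person SD. A patient enters if two consecutive readings among V earlier ones are below 106.7; with p the patient's own chance of a reading below the cut, that probability is p² for V = 2 and follows by recursion for larger V. Integrating over patients, and applying the power formulas of steps 1 and 3 at 300 per group, gives:

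| w | V | Control at later reading | Difference (points) | Power, control | MAP difference (mmHg) | SD | Power, MAP |
|---|---|---|---|---|---|---|---|
| 6 | 2 | 92.6% v 90.2% | 2.4 | 18% | 1.8 | 9.8 | 60% |
| 6 | 8 | 87.0% v 83.0% | 4.0 | 28% | 2.1 | 10.3 | 69% |
| 8 | 2 | 88.8% v 85.2% | 3.6 | 26% | 2.0 | 10.7 | 63% |
| 8 | 8 | 83.0% v 77.7% | 5.3 | 38% | 2.3 | 11.0 | 73% |
| 10 | 2 | 84.0% v 78.5% | 5.5 | 41% | 2.4 | 11.6 | 73% |
| 10 | 8 | 79.5% v 72.6% | 6.9 | 51% | 2.7 | 11.7 | 80% |

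Unselected values: 8.8 points and 68%; 3.2 mmHg and 90%. Selection also removes more of one group than the other: at w = 8 and V = 2, 66% of the functional group qualifies against 55% of the non-functional group.

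**7. Were the sizing data themselves restricted to controlled readings?** A normal distribution cut off above cannot have an SD larger than the gap from its mean to the cut. The gaps are 106.7 − 97.6 = 9.1 and 106.7 − 100.8 = 5.9 mmHg, both below 12. For roughly normal data, the readings behind the sample size were not limited to controlled ones.

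**The case against.** The strongest reply is that Section 9.0 is the eligibility list and has no control criterion. If it governs, uncontrolled patients can enrol and endpoint 1 varies normally. This stands. The selection operates only if the Study Summary and Section 4.0 prevail, and the documents do not settle which does.

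A reader might also infer that endpoint 1 is constant, or nearly so, on any reading. The documents do not support that. Section 4.0 asks only for a history of control, Section 5.0 records the most recent pressure, and at such a reading control is about 73–93%. If level of control means a continuous pressure, the endpoint is range-restricted, not constant. Nor does selection always remove most of the contrast: with w = 10 and V = 8, 6.9 of 8.8 points remain.

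A third inference is that a controlled-only sample could teach nothing about treatment success. That is too strong. Section 5.0 describes the design as relating variants to the drugs used to achieve control, and Section 16.0 regresses on drug class. Change in pressure, number of medications, time and visits to control still vary among controlled patients.

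Finally, admitting uncontrolled patients has consequences: primary endpoint 2 and secondary endpoints 1 to 3 run to control and are undefined for patients who never reach it. This stands and is dealt with in the fix.

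**Conclusion.** The defect is real but conditional. The Study Summary and Section 4.0 contradict Section 9.0 on whether control is an entry condition, and endpoint 1 has no defined reading. If control is required, endpoint 1 carries no information when read as control ever achieved. Read from the most recent pressure, it loses about a fifth to nearly three quarters of the genotype contrast (8.8 points down to 6.9 or 2.4). MAP loses about 16–45% of its 3.2 mmHg, and its power at 300 per group falls from 90% to about 60–80%. Part of that loss is absorbed because 300 exceeds the 221 that the stated inputs require.

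The direction holds in every scenario; the size rests on the assumed within-person SD and number of readings, on normality, and on MAP below 106.7 standing in for control. The documents do not say whether the patients behind the sizing data had a history of control. Step 7 shows only that the readings used were not confined to controlled ones.

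Removing the selection would not bring endpoint 1 to 80% power. The study was sized on MAP, and endpoint 1 has about 68% power at 300 per group even without selection.

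**What to change.** Remove the control requirement from the Study Summary and Section 4.0 so that the Section 9.0 list governs, and invite controlled and uncontrolled patients from the same record query. Then:

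- define primary endpoint 1 as control yes/no at the most recent blood pressure;
- measure primary endpoint 2 from baseline to that same reading;
- treat patients never controlled as censored for time to control and visits to control;
- report number of medications as the current number, by control status.

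The cost is redefining four endpoints, changing the protocol and invitation wording, and a somewhat wider mailing. No procedure is added for participants.

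If controlled-only entry is intended, add it to Section 9.0 and remove endpoint 1 as a primary endpoint. Limit the conclusion to which regimen is in use among controlled patients, and restate power for that population, for example about 65% at 300 per group if MAP is taken at a controlled reading. Either choice needs to be made before recruitment.

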5. N/A

5.0 Procedures Involved

1. Study Design: Retrospective analysis of association with DNA variants with pharmacotherapy used to achieve BP control.

General Flow of Activities:

1. Patients identified via UMN AHC-IE and sent recruitment letter, consent, survey and buccal swab kit via FRA's recruitment mailing process.
 - a. An E-mail, Letter, survey information, are included along with this submission.
2. Subject collects buccal swab:

Using the collection kit consisting of two buccal swabs and two uniquely barcoded tubes the investigator, patient, or designee will remove the first buccal brush and scrape the brush end across the inside of a Subject's right cheek repeatedly (for five seconds using moderate pressure). The investigator, patient, or designee will place the brush end over the open buffer vial and press the opposite end of the swab stick to release the brush into the buffer and then close the vial. The process will be repeated on the left cheek. Each of the right and left cheek vial numbers must be recorded on the clinical review form and accountability log as right (R), or left (L).

PROTOCOL TITLE:

VERSION DATE:

3. The patients return completed consent, buccal kit, to Geneticure for sorting.
4. The signed consent form is sent to the PI ([name]) and the buccal swab in lysis buffer is sent to the University of Arizona Genomics core facility for Genotyping.
 - All genotyping is performed in a blinded manner looking at 19 single nucleotide polymorphisms.
5. \$30 sent to participant at the time the Geneticure team receives the buccal swab, consent, etc. The Geneticure team will perform any follow-up needed for participants who do not receive their payment, additional questions. Clinical questions will be forwarded to [name] as the PI
6. Research team (Fairview pharmacy residents [name] and [name]) conducts chart review and abstracts data onto CRFs
7. CRFs sent to Geneticure

Specific Study procedures:

Screening

- Identify Potential Study Subjects through AHC. Refer to the Inclusion and Exclusion Criteria sections of this protocol for a complete list of eligibility criteria.
- Obtain Written Informed Consent either in-person or via mail. Each potential study participant must be given time to review the IRB-approved informed consent form, have his/her questions answered to their satisfaction and sign the form prior to any study procedures being performed. A subject will be given a copy of the informed consent form.
- Review Inclusion/Exclusion Criteria. The investigator and/or designee will review all criteria to determine if the subject is eligible for enrolment. Eligibility of all subjects must personally be confirmed by the Investigator and will be documented on the CRF.

Enrollment

- Assign Identification Number to Eligible Subjects.

Chart Review

- Record demographics, antihypertensive medical history and most recent blood Pressure. Data will be documented in the source document and recorded on the patient demographic form, including but not limited to the following:
 - Age
 - Sex

PROTOCOL TITLE:

VERSION DATE:

- Height
- Weight
- Race
- Ethnicity

(additional data for collection is included in the attachment entitled "metrics")

Specimen Collection

- Collect Buccal Specimen.

Subject Numbering

Subjects meeting the criteria for enrollment (and their specimens) will be identified by unique numbers that will be assigned sequentially by order of enrollment. The pre-assigned investigational site number will be prefixed with GCE and the identification number and separated by a hyphen (e.g., GCE-001etc.). Throughout the descriptions within the protocol the A swab will be referring to the swab that has originated from the right cheek, while the B swab will be that that has originated from the left cheek. To further clarify. Subject GCE-001 will be given two barcoded tubes. These barcode numbers should be recorded for each patient. These will also be recorded as originating from the right cheek (A) or left cheek (B).

At no time should any study paperwork or specimens be marked with the subject's name or any other traceable identifier except for the informed consent form, which is signed by the subject and kept at the site. At no time should the original (signed) or a copy of this form be collected by the Sponsor or its representative.

2. Follow-Up: Data will be collected for up to one year.
3. Individually Identifiable Health Information: a chart review will be performed to assess a patient's BP medication history. No personally identifiable information (Name, Address, date of birth) will be kept with the study document. The only individuals who will have access to a patient's chart will be Fairview clinical employees who also have IRB approval to be involved with this study. The linking information (from consent) will be kept in the PI ([name]) office in a locked cabinet. No patient data with identifying information will be transmitted outside of the Fairview system. Additionally, no de-

PROTOCOL TITLE:

VERSION DATE:

identified PHI will be transmitted to any individual who does not have IRB approval to be involved with this research study.

4. Use of radiation: *N/A*
5. Use of Center for Magnetic Resonance Research: *N/A*

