6.0 Data and Specimen Banking

If this study does not involve data or specimen banking for future use, type "N/A" and delete the sub-headings below. Otherwise, complete all items below.

1. Storage and Access: Data will be stored on secure, password-protected Fairview Health Services Servers.
2. Data: BP control history and relevant cardiovascular and side-effect data will be collected. We will not be banking any of this information for other studies, this is for the present study only.
3. Release/Sharing: No individual data or patient information will be released or shared with any individual who is not approved to participate in this research study.

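### Change in blood pressure from baseline is a primary measure, but baseline is undefined, no model is stated for the change, and baseline pressure is not among the listed confounders

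*Combined protocol and SAP*

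**What the plan says.** - **Endpoint.** Section 3.0 lists two primary measures: the level of control (<140/<90) and "Change in blood pressure from baseline to control". The Study Summary and section 1.0 repeat the second. None of them says which reading is baseline.
- **Data.** The Chart Review step in 5.0 reads "Record demographics, antihypertensive medical history and most recent blood Pressure". The most recent pressure is the only reading named. The list is open, however: it adds that "additional data for collection is included in the attachment entitled" metrics, and that attachment is not part of the document. Section 6.0 says "BP control history and relevant cardiovascular and side-effect data will be collected", and 4.0 describes a "clinical chart review of the patient’s hypertension and medication history".
- **Analysis.** Section 16.0 describes two models. A univariate regression estimates the "magnitude of linearity between drug class that yielded the best blood pressure control and genetic profile of the subject". The second is adjusted: "Multiple regression analysis will be performed to determine the impact of confounding variables (height, weight, age, race) on blood pressure control". Neither names change in pressure as its outcome, and baseline pressure is a covariate in neither.
- **Population.** The Study Summary and 4.0 describe patients who have reached control, which 4.0 sets at <140/<90 on two consecutive office measures. The inclusion criteria in 9.0 do not list control.

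**The concern.** A change score needs a starting value, and here the finishing value is constrained: the endpoint stops at control, and the patients are described as controlled. When the end is held below a ceiling, most of the room for variation lies in the start. Patients who began higher then show larger falls, whatever their genotype or drug.

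This affects the study's question if starting pressure differs between the groups compared. Section 4.0 describes the panel genes as known to influence blood pressure, so a baseline difference by genotype is plausible. Drug classes were chosen by clinicians, so a difference by class is plausible too. An unadjusted comparison of change could then present initial severity, with regression to the mean, as a genotype-specific response to treatment. The plan names four confounders and leaves out the one most directly tied to this endpoint. Anyone following it as written would leave starting severity unadjusted.

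**Working it through.** **The plan's own figure.** There is none for the change endpoint. The power section in 16.0 works from on-treatment mean arterial pressure (WNK-1: 97.6 against 100.8 mmHg, pooled SD 12) and arrives at 300 per group. It gives no SD of baseline, no SD of change and no baseline-to-final correlation. Only the 300 per group is used below.

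**Assumed inputs (systolic, mmHg).** Baseline B: mean 150-160, SD 15. Treated value F: mean 132, SD 12. Correlation r between B and F: 0.3-0.5. Let the reduction be R = B − F.

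**Step 1. Dependence of change on baseline, no cap.**
- SD(R) = √(15² + 12² − 2·r·15·12)
- corr(R, B) = (15 − 12r) / SD(R)
- r = 0.3: SD(R) = √261 = 16.16; corr = 11.4/16.16 = 0.706; share of variance 50%.
- r = 0.5: SD(R) = √189 = 13.75; corr = 9.0/13.75 = 0.655; share 43%.

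Over a wider grid (SD of B 12-20, SD of F 8-12, r 0-0.5), the uncapped share runs from 25% to 86%. The 25% arises with both SDs at 12 and r = 0.5: SD(R) = 12, corr = (12 − 6)/12 = 0.50, and 0.50² = 0.25.

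**Step 2. The same with the end value capped (simulation).**

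| Restriction | corr(R, B) | Share of variance in R |
|---|---|---|
| Treated systolic <140 only | 0.80-0.83 | 64-69% |
| Treated <140 and baseline ≥140 | 0.72-0.79 | 52-62% |

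A second set of assumptions (means 155 and 137, SD of B 12-16, SD of F 12, r 0.3-0.5, treated <140) gives 57-77%.

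**Step 3. What a baseline difference does to unadjusted change.** Suppose two groups differ by d at baseline and not at all in final pressure given baseline. The expected difference in R is d × (1 − r·12/15).
- r = 0.3: multiplier 0.76, so d = 2 gives 1.52 and d = 5 gives 3.80.
- r = 0.5: multiplier 0.60, so d = 2 gives 1.20 and d = 5 gives 3.00.

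With 300 per group, SE = SD(R) × √(2/300), which is 1.319 (r = 0.3) or 1.122 (r = 0.5). The chance of a two-sided p < 0.05 is close to Φ(difference/SE − 1.96).

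| r | d | Spurious difference | Difference/SE | Declared significant |
|---|---|---|---|---|
| 0.3 | 2 | 1.52 | 1.15 | 21% |
| 0.3 | 5 | 3.80 | 2.88 | 82% |
| 0.5 | 2 | 1.20 | 1.07 | 19% |
| 0.5 | 5 | 3.00 | 2.67 | 76% |

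Step 3 applies no cap and no multiplicity correction. The correction that 16.0 promises would lower the last column.

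**The case against.** **Is only the latest reading captured?** A reader might infer from 5.0 that no baseline is abstracted. The document does not support this. The list is open, the metrics attachment cannot be seen, 6.0 promises a history of control, and 4.0 covers the hypertension history. It also matters which case applies: with no baseline the change cannot be computed, and with one the question is adjustment. What stands is that the available text neither defines baseline nor names it as a field.

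**Is an unadjusted analysis of change planned?** Not explicitly. The adjusted model in 16.0 has control as its outcome, and no model is named for change. The defect is an unspecified analysis together with a confounder list that omits baseline.

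**Does the response mainly reflect how high pressure started?** That is tempting given 52-69%, but it rests on assumed means, SDs and correlations and on the cap. Without the cap the share can fall to 25%, and 9.0 does not require control. Variance explained within patients is also not bias between groups. Bias needs a baseline difference between the groups, which is plausible but not quantified anywhere in the document.

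**Would adjustment save many subjects?** A reader might infer so by comparing adjusted with unadjusted change. The plan is powered on on-treatment pressure, not on change, and selection on the end value weakens the baseline-to-final correlation. No saving is claimed here.

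**Is covariate adjustment the right answer?** Groups are not randomised, so adjusted and unadjusted results answer different questions when baselines differ (Lord's paradox). A noisy chart baseline leaves residual bias, and adjustment does not undo selection on the end value. This objection stands. It argues for stating the model in advance and showing both results, not for leaving the analysis unstated.

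**Conclusion.** The concern holds as a gap in specification that has a foreseeable bias. A primary measure has no defined starting value in the available text and no stated model, and the listed confounders omit the starting value.

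The change depends heavily on baseline if the end value is held below 140: about 52-69% of variance for systolic pressure with baseline mean 150-160 (SD 15), treated mean 132 (SD 12) and r 0.3-0.5. If groups differ by an assumed 2-5 mmHg at baseline and not in final pressure given baseline, unadjusted change shows a spurious difference of about 1.2-3.8 mmHg, significant in about 19-82% of studies at 300 per group. These figures illustrate the risk. The document supplies none of the SDs, correlations or baseline differences behind them, so they do not show that bias of this size will occur. The change should be made, with medium confidence in the size of the effect.

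**What to change.** - **5.0 Chart Review:** define baseline as the last office pressure before the first antihypertensive prescription, and list it as a field together with its date. If the metrics attachment already holds it, say so in the text.
- **16.0 Data Analysis Plan:** add baseline pressure to the covariate list. State the model for the second primary measure as on-treatment pressure with baseline as a covariate, and report unadjusted change beside it because the groups are not randomised.
- **16.0 Missing Data:** report how many subjects have no pre-treatment reading and state how they are handled. The present text offers only an available-data analysis and rules out sensitivity analyses on missing data.

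**Cost.** One or two extra fields from charts that are already being read. Diagnosis must be at least one year old with no upper limit, so some baselines will be old, noisy or absent, and some confounding will remain after adjustment.
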